# 4.2 Scientific Rationale for Study Design

A randomised, controlled, examiner-blind, parallel group design is a recognised approach for investigating the clinical efficacy of a product for the relief of DH (Holland, 1997).

The longer-term clinical efficacy of the sponsor's 0.454% SnF2 toothpastes is currently supported by two 8-week DH studies conducted outside China (Parkinson et al, 2013; Parkinson et al, 2015). Longer-term DH studies evaluating an alternative occlusion technology (CSPS) in China employed a longer treatment period (Hall et al, 2017 11 weeks; CCI III In order to establish longitudinal performance for the test toothpaste, with greater opportunity for its clinical benefits to be observed, a 12 week treatment period will be employed here (Murray, 1994; Irwin, 1997). To comply with Chinese MoH guidelines for the testing of functional (desensitising) toothpastes, a single interim assessment timepoint will be included after 6 weeks' treatment ('Sensitivity levels are to be examined and recorded at the baseline, mid-trial and end-trial stages'; Ministry of Health (China), 2010).

In line with published recommendations for the design and conduct of DH studies (Holland, 1997) and the requirements of the Chinese MoH guidelines for the testing of functional (desensitising) toothpastes (Ministry of Health (China), 2010), two independent stimuli will be employed (tactile and thermal (evaporative air) stimuli) to evaluate the efficacy of the 0.454%  $SnF_2$  toothpaste. To avoid inter-assessor variability, the same clinical examiner should be responsible for the administration of a given stimulus (tactile or evaporative (air)) and the conduct of the associated examiner-assessed DH measure from Screening until the end of the study. DH will be assessed at Screening, Baseline (pre-treatment) and following 6 and 12 weeks of treatment.

The age range over which an individual can experience DH is wide (early teens to 70s) (Fischer et al, 1992), with peak incidence known to occur between the ages of 20-40 years (Flynn et al, 1985). The fall in prevalence observed in later decades reflects age-related changes in the dentine and pulp of the tooth which act to reduce both dentine permeability and the tooth's response to external triggers of DH (Pashley, 2008; Seltzer and Bender, 1975). The dental pain experienced by much older members of the population is less likely to be diagnosed as DH (Rees, 2000), thus an age range of 18-70 years has been selected for this study to target individuals with tooth sensitivity due to DH.

While there is no published evidence to indicate that gender impacts the pathophysiology of DH, a national DH survey conducted in rural China in 2009 reported a greater proportion of females with DH compared to males (female 35.8%; male 23.4%) (Liang, 2017). To ensure the current study population is representative of the Chinese population being studied, the study site will aim to recruit a female:male ratio of approximately 3:2.

According to ICH guidelines (ICH E6 (R2) Good clinical practice | European Medicines Agency (europa.eu), for a study to be classed as double blind, the subject, investigator, clinical examiners, monitors, data analysts, and staff involved in determining subject eligibility/ assessing compliance should be blinded to the treatment a subject receives. However, given it will not be possible to ensure identical appearance, flavour and packaging for the three commercial toothpastes to be evaluated in this study, the study is described as 'examiner blind'.

In line with the Chinese MOH guidelines (Ministry of Health (China), 2010) for the testing of functional (desensitising) toothpastes, a regular fluoride toothpaste with no known (or claimed) anti-sensitivity efficacy will be included as the negative control (Crest Cavity Protection Fresh Lime; China commercial product). In addition, a 5.0% CSPS toothpaste (Sensodyne Repair & Protect; China commercial product) with proven DH efficacy in the Chinese population (in

Property of GSK Consumer Healthcare - Confidential

May not be used, divulged, published or otherwise disclosed without the consent of GSKCH

Clinical Protocol Template v9.0

Page 18 of 73

clinical studies that satisfied current (at time of writing) Chinese MoH guidelines: sponsor clinical studies Hall et al, 2017 and CCI will be included in the study as a positive control (i.e., as a benchmark of performance in the Chinese population for 'study validation'). Given the primary objective is to demonstrate statistical superiority for the test toothpaste compared to negative control in change from Baseline in Schiff sensitivity score at Week 12, qualifying subjects will be randomised to study treatment using a 2:2:1 allocation ratio (Test: Negative Control: Positive Control).

Subjects using anti-sensitivity products as part of their normal oral hygiene routine will be excluded (their own oral hygiene products will be checked for presence of known anti-sensitivity ingredients at Screening); if they are continuing to experience DH, they are unlikely to respond to use of a sensitivity toothpaste in the current study.

Subjects will be asked to describe their typical daily oral care regimen at Screening. To help maintain study product in the oral cavity for the duration of each timed brushing, any subject who habitually rinses with water during toothbrushing (self-reported) will be excluded from the study. Similarly, at Baseline, following review of the brushing videos, any subjects who rinsed during brushing with the acclimatisation toothpaste will be excluded.

Clinical trials evaluating pain-related end points can be prone to 'placebo effects' (Addy, 1985; West, 1997); such effects are frequently observed in DH studies. A study conducted to evaluate the natural history of the DH condition also highlighted the existence of a 'no treatment' effect, characterised by an improvement in sensitivity simply as a result of study participation (Leight, 2008). Analyses of sponsor data from earlier DH efficacy studies indicate (i) subjects with a lower frequency of DH symptoms may exhibit greater 'placebo'/ 'no treatment' effects (sponsor clinical study: 216953) and (ii) subjects with different qualifying Schiff sensitivity scores at Screening and Baseline for one or both test teeth may also exhibit greater 'placebo'/ 'no treatment' effects (sponsor clinical study: 216954).

To help minimise the potential impact of such effects:

CCI

- An acclimatisation period (2-4 weeks) will precede the Baseline visits. During this period, study subjects will brush twice daily with the regular fluoride toothpaste and toothbrush provided (in place of their normal oral hygiene products) and record each timed brushing occasion in a diary. The acclimatisation period will also help standardise oral hygiene practice across the study population prior to treatment.
- Subjects will complete a Screening Questionnaire (Appendix 15.2) at Visit 1; those who report experiencing DH symptoms only 'several times a month', 'once a month' or 'less than once a month' will be excluded from the study.
- Each selected test tooth must have the same qualifying Schiff sensitivity score at the Screening and Baseline visits (i.e., Schiff sensitivity score = 2 at Screening and Baseline, or Schiff sensitivity score = 3 at Screening and Baseline).

On completion of the Baseline assessments, the clinical examiner will select two test teeth from those that qualified at Screening (Visit 1) and Baseline (Visit 2) for assessment of tactile and evaporative (air) sensitivity at all subsequent visits (Table 4-1). The selection of two 'test teeth' to evaluate changes in DH is common practice in sensitivity studies (Schiff, 1994). Qualifying subjects will be stratified according to the maximum Schiff sensitivity score of their two selected test teeth to ensure treatment groups are balanced for DH severity.

DH is an episodic condition; symptoms are known to vary spontaneously (West, 2008, West et al., 2013). Baseline clinical values that would support enrolment may represent random highs

Property of GSK Consumer Healthcare - Confidential

May not be used, divulged, published or otherwise disclosed without the consent of GSKCH

Clinical Protocol Template v9.0

Page **19** of **73** 

that could be followed by regression to the mean, leaving the subject or selected test tooth without the condition under investigation during the treatment period. To help minimise the potential for this to occur on the current study, randomised subjects will be required to demonstrate consistency in DH response at both the Screening and Baseline visits.

- Randomised subjects must have a minimum of two eligible teeth (no dentition exclusions, presence of EAR, MGI = 0 adjacent to the test area only, clinical mobility = 0) with a tactile threshold ≤ 20 g and a Schiff sensitivity score ≥ 2 at both Screening and Baseline.
- Test teeth can only be selected from eligible teeth identified at Screening (no dentition exclusions, presence of EAR, MGI = 0 adjacent to the test area only, clinical mobility = 0), with a tactile threshold ≤ 20 g and a Schiff sensitivity score ≥ 2 at both Screening and Baseline and with VAS ≥ 40 mm at Baseline only.
- Test teeth must have the same Schiff sensitivity score at Screening and Baseline.

Screening Assessments (Visit 1)						Baseline Assessments (Visit 2)				
Dentition Exclusions	EAR	MGI*	Clinical Mobility	Tactile Threshold	Schiff Sensitivity Score	Eligible Tooth	Tactile Threshold	Schiff Sensitivity Score	VAS	Test Tooth
None	Yes	0	0	$\leq$ 20g	2	Yes	$\leq$ 20g	2	$\geq$ 40mm	Yes
None	Yes	0	0	$\leq$ 20g	3	Yes	$\leq$ 20g	3	$\geq$ 40mm	Yes
None	Yes	0	0	$\leq$ 20g	2	Yes	$\leq 20g$	3	$\geq$ 40mm	No
None	Yes	0	0	≤20g	3	Yes	≤20g	2	$\geq$ 40mm	No

Table 4-1Eligibility Checks for Test Tooth Selection

#### Eligibility against each selection criterion is determined sequentially.

\*Adjacent to the test area only

VAS is completed at Screening and Baseline, but is a qualifying measure for Test Tooth Selection at Baseline **ONLY**.

# 4.3 Justification for Dose

Study products are toothpastes, intended for topical oral use, and will be applied by toothbrushing using a manual toothbrush.

The usage regimen of twice daily brushing (morning and evening) will be the same for all subjects, based on widely recommended oral hygiene practice and typical consumer habit. Study subjects will brush for 1-timed minute with their assigned study toothpaste on each brushing occasion in line with typical brushing times specified for similar DH efficacy studies (Parkinson, 2011; Makin, 2013; Hall et al., 2017; Docimo et al., 2009). Subjects allocated to the test toothpaste will be instructed to brush their two test teeth first, to ensure their sensitive teeth are treated, then their whole mouth for 1-timed minute. The usage regimen specified for the negative and positive control products is aligned with the usage instructions provided on the commercial packaging of both toothpastes.

After 12 weeks  $(85 \pm 4 \text{ days})$  twice daily usage, each subject should complete between 162-178 brushings with their randomized product. Subjects will complete a supervised brushing with their assigned study toothpaste at the end of each study visit (while still at the study site) to

Property of GSK Consumer Healthcare - Confidential

May not be used, divulged, published or otherwise disclosed without the consent of GSKCH

Clinical Protocol Template v9.0

Page 20 of 73

enable staff to confirm correct usage and to encourage compliance with the required usage regimen for the duration of the study.

Tongue cleaning forms an integral part of typical oral hygiene practice for many Chinese consumers; it will be permitted during the current study (using the toothbrush provided), after completing each 1-minute toothbrushing with study toothpaste but before the 10ml water rinse. Tongue brushing is not permitted while toothbrushing.

To help ensure the study toothpaste is retained in the oral cavity for the 1-minute brushing time, subjects must not rinse with water or expectorate during toothbrushing.

A recent consumer study (sponsor data on file) observed rinsing with variable, often copious amounts of water following toothbrushing to be common practice in Chinese consumers. To standardise rinsing practice across the study population, all subjects will be instructed to rinse once with water (10 ml dispensed from a dosing cup) after each brushing occasion.

# 4.4 End of Study Definition

A subject will be considered to have completed the study if they have completed all phases of the study including the last visit or the last scheduled procedure shown in the Schedule of Activities.

The end of this study is defined as the date of the last scheduled procedure, as described in the Schedule of Activities (Table 1-1), for the last subject.

# 5 STUDY POPULATION

# 5.1 Type and Planned Number of Subjects

The study will be conducted in a Chinese population (in China). Subjects will be male or female, with a minimum of 20 natural teeth, a self-reported history of tooth sensitivity and at least two teeth with clinical examiner-confirmed DH (tactile threshold  $\leq 20$  g and Schiff sensitivity score  $\geq 2$  at both Screening and Baseline; VAS  $\geq 40$  mm at Baseline). In addition, the selected test teeth must demonstrate a consistent response to the evaporative (air) stimulus at the Screening and Baseline visits (Schiff sensitivity score = 2 at Screening and Baseline, or Schiff sensitivity score = 3 at Screening and Baseline).

Sufficient subjects will be screened to randomize approximately 240 subjects to study treatment to ensure approximately 235 subjects complete the study (approximately 94 each for test toothpaste and negative control, and 47 for positive control), allowing for approximately 2% dropouts after randomization, as observed in previous clinical studies conducted in China.

Whilst the study products are not contra-indicated for pregnancy and breastfeeding, pregnant and/or lactating females will be excluded from this study due to the increased prevalence and severity of gingivitis and periodontal disease observed during pregnancy (Samant et al., 1976) and breastfeeding (Aghazadeh et al, 2019) which, together with the increased amounts of calculus and plaque observed during pregnancy, could impact DH assessments (Samant et al., 1976).

An enrolled subject is one who has agreed to participate in the clinical study following completion of the informed consent process (directly or via their legally authorized representative) and successfully met the eligibility criteria to proceed beyond the screening visit as described in the protocol design.

Property of GSK Consumer Healthcare - Confidential

May not be used, divulged, published or otherwise disclosed without the consent of GSKCH

Clinical Protocol Template v9.0

Page 21 of 73

This study can fulfill its objectives only if appropriate subjects are enrolled. The following eligibility criteria are designed to select subjects for whom participation in the study is considered appropriate. All relevant medical and non-medical conditions should be taken into consideration when deciding whether a subject is suitable for this protocol.

Subject eligibility to participate in the clinical study should be reviewed and documented by an appropriate member of the investigator study team before a subject is included in the study.

# 5.2 Inclusion Criteria

An individual must meet all of the following inclusion criteria to be eligible for enrollment into the study:

- 1. Provision of a signed and dated informed consent document indicating that the subject has been informed of all pertinent aspects of the study before any study procedures are performed.
- 2. Male or female who, at the time of screening, is between the ages of 18 to 70 years inclusive.
- 3. Subject who is willing and able to understand and comply with scheduled visits, product usage requirements and other study procedures.
- 4. Subject in good general, oral and mental health with, in the opinion of the investigator or medically qualified designee, no clinically significant or relevant abnormalities in medical history, or upon oral examination, that would impact the subject's safety or wellbeing, or the outcomes of the study, if they were to participate in the study, or affect the subject's ability to understand and follow study procedures and requirements.
- 5. Subject who owns a smartphone with WeChat application installed.

### 6. At Screening (Visit 1)

Subject must have:

- a) Self-reported history of tooth sensitivity lasting more than 6 months but not more than 10 years and experience DH symptoms at least 'once a week' or more frequently (Screening Questionnaire, Appendix 15.2).
- b) Good general oral health, with a minimum of 20 natural teeth.
- c) Minimum of **two** accessible, non-adjacent teeth (incisors, canines, pre-molars), preferably in different quadrants, with clinically confirmed DH.

Each eligible tooth must meet all the following criteria:

- i. Exposed dentine due to facial/cervical erosion, abrasion or gingival recession (EAR).
- ii. MGI = 0 directly adjacent to the exposed dentine (i.e., the test area) only.
- iii. Clinical mobility = 0.

CCI

iv. DH as evidenced by qualifying levels of tactile and evaporative (air) sensitivity (tactile threshold  $\leq 20g$  and Schiff sensitivity score  $\geq 2$ ).

Property of GSK Consumer Healthcare - Confidential

May not be used, divulged, published or otherwise disclosed without the consent of GSKCH

Clinical Protocol Template v9.0

Page 22 of 73

#### 7. At Baseline (Visit 2):

All teeth identified at Screening (Visit 1) as eligible for Baseline assessments will be reassessed for tactile sensitivity first; eligible teeth with Baseline tactile threshold  $\leq 20$ g will then be re-assessed for evaporative (air) sensitivity.

Subjects must have:

A minimum of two non-adjacent, accessible teeth (incisors, canines, pre-molars), preferably in different quadrants, with clinically confirmed DH as evidenced by qualifying levels of tactile and evaporative (air) sensitivity:

- a) Tactile threshold  $\leq 20g$  at Screening and Baseline
- b) Schiff sensitivity score  $\geq 2$  at Screening and Baseline.
- c) VAS  $\geq$  40 mm at Baseline.

The clinical examiner will select two 'test teeth' from those eligible teeth which meet the tactile threshold and Schiff sensitivity score criteria at both Screening and Baseline, and the VAS criterion at Baseline.

Each test tooth must demonstrate a consistent DH response to the evaporative (air) stimulus at both Screening and Baseline:

Screening Schiff sensitivity score = $2 \text{ and }$ Baseline Schiff sensitivity score = $2$
OR
Screening Schiff sensitivity score = 3 and Baseline Schiff sensitivity score = 3

The procedure for selecting test teeth is summarised in **Table 4-1**.

# 5.3 Exclusion Criteria

An individual who meets any of the following exclusion criteria will be excluded from the study:

- 1. Subject who is an employee of the study site, either directly involved in the conduct of the study or a member of their immediate family; or an employee of the study site otherwise supervised by the investigator; or a sponsor employee directly involved in the conduct of the study or a member of their immediate family.
- 2. Subject who is participating in, or has participated in, other studies (including non-medicinal studies) involving investigational product(s) within 30 days of Screening (Visit 1).
- 3. Subject who is participating in, has participated in, a study evaluating a tooth desensitising treatment within 8 weeks of Screening (Visit 1).
- 4. Subject who is using, or has used, an oral care product indicated for DH relief within 8 weeks of Screening (Visit 1). Subjects will be required to bring their current oral care products to Visit 1 for staff to verify the absence of known anti-sensitivity ingredients and DH claims.
- 5. Subject who has had a professional de-sensitising treatment within 8 weeks of Screening (Visit 1).
- 6. Subject who habitually rinses with water during toothbrushing (self-reported at Screening (Visit 1)).
- 7. Subject seen to rinse with water while brushing with the acclimatization toothpaste during

Property of GSK Consumer Healthcare - Confidential

May not be used, divulged, published or otherwise disclosed without the consent of GSKCH

review of their brushing compliance videos at Baseline (Visit 2).

- 8. Subject with known or suspected intolerance or hypersensitivity to the study products or any of their stated ingredients (or closely related compounds).
- 9. Subject who is unwilling or unable to comply with product usage instructions (Section 4.3) or Lifestyle Considerations (Section 5.5) as described in the protocol.
- 10. Female subject who is pregnant or intending to become pregnant during the study (self-reported).
- 11. Female subject who is breastfeeding.
- 12. Subject with a recent history (within the last year) of alcohol and/or substance abuse.
- 13. Subject with, in the opinion of the investigator or medically qualified designee, an acute or chronic medical or psychiatric condition or laboratory abnormality that may increase the risk associated with study participation or study product administration or may interfere with the interpretation of study results and, in the judgment of the investigator or medically qualified designee, would make the subject inappropriate for entry into this study.
- 14. Subject taking daily doses of medications or traditional herbal treatments which, in the opinion of the investigator or medically qualified designee, could interfere with their perception of pain.
  - Examples of such medications include analgesics, anticonvulsants, antihistamines that cause marked or moderate sedation, sedatives, tranquilisers, anti-depressants, mood-altering and anti-inflammatory drugs.
  - Examples of herbal treatments include clove oil, olive oil or other treatments directly applied to the oral cavity for the treatment of oral health conditions.
- 15. Subject taking daily doses of a medication which, in the opinion of the investigator or medically qualified designee, is causing xerostomia.
- 16. Subject who requires antibiotic prophylaxis for dental procedures.

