#### 18. At Baseline (Visit 2)

Subject who has taken antibiotics within 2 weeks of their Baseline visit (during the acclimatisation period).

- 19. Subject who has had a professional or self-applied tooth bleaching procedure within 8 weeks of Screening (Visit 1).
- 20. Subject who has had dental prophylaxis within 4 weeks of Screening (Visit 1).
- 21. Subject who has had treatment for periodontal disease (including surgery) within 12 months of Screening (Visit 1).
- 22. Subject who has had scaling or root planning within 3 months of Screening (Visit 1).
- 23. Subject with a tongue or lip piercing.

24. Subject with, in the opinion of the investigator or medically qualified designee, gross periodontal disease.

Property of GSK Consumer Healthcare - Confidential

May not be used, divulged, published or otherwise disclosed without the consent of GSKCH

Clinical Protocol Template v9.0

Page 24 of 73

- 25. Subject with evidence of gross intra-oral neglect or the need for extensive dental therapy.
- 26. Subject with a fixed or removable partial prosthesis which, in the opinion of the investigator or medically qualified designee, would impact study outcomes.
- 27. Subject with multiple dental implants which, in the opinion of the investigator or medically qualified designee, would impact study outcomes.
- 28. Subject with fixed or removable orthodontic braces/bands or a fixed orthodontic retainer.

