# 5.5 Lifestyle Considerations

If, in the opinion of the investigator or medically qualified designee, a subject has not complied with a study restriction (oral hygiene, dietary or alcohol-related) prior to a study visit or cannot attend a study visit, every effort will be made to reappoint them within the permitted visit tolerances (see Schedule of Activities, Table 1-1). The reason for re-appointment will be documented in the electronic case report form (eCRF).

Property of GSK Consumer Healthcare - Confidential

May not be used, divulged, published or otherwise disclosed without the consent of GSKCH

Clinical Protocol Template v9.0

Page 25 of 73

If re-appointment is not possible, the following visit specific actions should be taken:

- **Baseline (Visit 2):** if the subject cannot be reappointed (within the 2-4 week visit tolerance), they will be withdrawn from the study. No clinical efficacy assessments will be performed. The subject may be replaced.
- Week 6 (Visit 3): if the subject cannot be reappointed (within the visit tolerance) the subject will continue in the study. No clinical efficacy assessments will be performed.
- Week 12 (Visit 4): if the subject cannot be reappointed (within the visit tolerance), they will be withdrawn from the study. No clinical efficacy assessments will be performed. The subject will not be replaced.

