### For the Duration of the Study: Screening (Visit 1) to Subject's Last Study Visit

- Subjects should delay any non-emergency, elective dental treatments until after study completion (including dental prophylaxis).
- Should a randomized subject start a course of treatment which includes daily, regular or intermittent use of any medication, details of that medication/treatment will be recorded in the eCRF. The investigator, or their medically qualified designee, will decide if the subject can continue on the study or should be withdrawn.
- Should a subject take a medication which, in the opinion of the investigator or their medically qualified designee, could impact the subject's perception of DH (e.g., an analgesic) within 8 hours of a scheduled study visit, the medication should be recorded in the eCRF and every effort will be made to reappoint them within permitted visit tolerances (see Schedule of Activities, Table 1-1). The reason for re-appointment will be documented in the eCRF.

If re-appointment is not possible, the following visit specific actions should be taken:

- Screening (Visit 1): the subject will be withdrawn from the study. No tooth sensitivity assessments will be performed. The subject may be replaced.
- **Baseline (Visit 2):** the subject will be withdrawn from the study. No tooth sensitivity assessments will be performed. The subject will not be replaced.
- Weeks 6 & 12 (Visits 3 & 4): the subject will continue in the study. Tooth sensitivity assessments will be performed.

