## 15.3 Video Compliance Check-list

Did the subject only use the study products provided?	Yes	No*
Did the subject use the correct amount of toothpaste (full toothbrush head)?	Yes	No*
Did the subject brush according to the acclimatisation product usage instructions?		No*
Did the subject rinse with water during tooth brushing?	Yes**	No
Did the subject rinse with the correct amount of water after brushing?		No*
If the subject brushed their tongue, did they do this after toothbrushing? N/A (circle if subject did not brush their tongue)	Yes	No*

\*Non-compliant response; re-instruct in correct product usage procedure

\*\* Non-compliant response; exclude

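### Dental and desensitising look-backs are timed to Screening, and the run-in rules do not clearly exclude a subject treated or exposed before Baseline

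*Protocol*

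**What the plan says.** Protocol Section 5.3 sets these look-backs, all counted from Screening (Visit 1):

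- Criterion 4: "Subject who is using, or has used, an oral care product indicated for DH relief within 8 weeks of Screening (Visit 1"
- Criterion 5: "Subject who has had a professional de-sensitising treatment within 8 weeks of Screening (Visit 1"
- Criterion 19: "Subject who has had a professional or self-applied tooth bleaching procedure within 8 weeks of Screening (Visit 1"
- Criterion 20: prophylaxis, 4 weeks
- Criterion 21: periodontal treatment, 12 months
- Criterion 22: scaling or root planing, 3 months

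Section 8.1 puts Screening 14-28 days before randomisation. Two topics do have a criterion reaching into the run-in. One is antibiotics, where criterion 18 adds to criterion 17: "Subject who has taken antibiotics within 2 weeks of their Baseline visit". The other is rinsing, where criterion 7 (run-in videos) adds to criterion 6 (self-report at Screening).

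The run-in has other rules. Section 5.5.1 bars all oral care products not supplied by the study, bleaching products included. If a restriction was broken before Baseline, Section 5.5 calls for re-appointment, and "if the subject cannot be reappointed (within the 2-4 week visit tolerance), they will be withdrawn from the study". Section 6.7 excludes subjects seen rinsing during brushing and re-instructs for every other departure from usage requirements. Appendix 15.3 follows this: a wrong answer to "Did the subject only use the study products provided" is marked for re-instruction, and only rinsing is marked for exclusion. On dental care, Section 6.8 says: "Subjects should delay any non-emergency, elective dental treatments until after study completion (including dental prophylaxis". It states no consequence for dental treatment received before randomisation.

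**The concern.** The documents do not explain the look-back windows. The natural purpose is that a subject should reach the efficacy baseline free of recent desensitising or dental treatment. That baseline is Visit 2, so a window that ends at Visit 1 leaves the last two to four weeks to other rules. Those rules either state no consequence (6.8) or state one that keeps the subject in (5.5, 6.7, Appendix 15.3).

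Section 4.2 justifies excluding users of anti-sensitivity products on the ground that "if they are continuing to experience DH, they are unlikely to respond to use of a sensitivity toothpaste in the current study". A subject exposed during the run-in who still qualifies at Baseline may resemble that group and dilute the difference between test toothpaste and negative control. Other recent dental treatment could add change unrelated to the study product in every arm.

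Once randomised, such a subject stays in the mITT primary analysis. A per-protocol analysis is run only if that population differs from mITT by more than 10% (Protocol 12.2.2, SAP 4.1.3), so a small number of cases would not trigger it.

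**Working it through.** **1. Time from treatment to Baseline.** Inputs are the look-backs in Section 5.3 and the 14-28 day run-in in Section 8.1. For a subject who just clears a look-back counted backward from Screening, the gap at Baseline is the look-back plus the run-in.

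| Case | Calculation | Days before Baseline |
|---|---|---|
| Just clears 8 weeks (criteria 4, 5, 19) | 56 + 14 to 56 + 28 | 70-84 |
| Just clears 4 weeks (criterion 20) | 28 + 14 to 28 + 28 | 42-56 |
| Exposed during the run-in | 0 to 28 | 0-28 |

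Re-appointment under Section 5.5 must stay within the 2-4 week tolerance. Even exposure right after Screening is therefore at most 28 days old at Baseline. Re-appointment cannot recover the minimum of 70 days implied by the 8-week rule.

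**2. Which rule applies to a run-in event.**

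| Event | Rule | Stated consequence before randomisation |
|---|---|---|
| Professional desensitising, in-office bleaching, prophylaxis, periodontal treatment, scaling | 6.8, request to delay elective care | None stated; depends on how the Screening window is read and on investigator opinion (criterion 31) |
| Own DH or bleaching product | 5.5.1, prohibited | Re-appoint, otherwise withdraw (5.5); re-instruct (6.7, Appendix 15.3 item 1) |
| Antibiotics | Criterion 18 | Excluded if within 2 weeks of Baseline |
| Rinsing seen on video | Criterion 7 | Excluded |

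**3. The plan's power figure.** Protocol 12.1 gives 94 per arm, mean difference 0.3, SD 0.6 and two-sided 5%. The effect size is 0.3/0.6 = 0.5. For the two-sample t-test, df = 2 × 94 − 2 = 186 and the noncentrality is 0.5 × √(94/2) = 3.43. Power is 92.65%, as stated.

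**4. Illustration only.** Suppose a share p of subjects gains nothing over negative control, with SD and n unchanged. The effect size is then 0.5 × (1 − p).

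| Assumed p | Effect size | Power |
|---|---|---|
| 0% | 0.500 | 92.65% |
| 2% | 0.490 | 91.7% |
| 5% | 0.475 | 90.0% |
| 10% | 0.450 | 86.6% |

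Neither p nor the zero-benefit assumption comes from the documents.

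**The case against.** The run-in is regulated, and several provisions could catch these subjects.

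- **The window may reach forward.** A procedure on run-in day 10 is literally within 8 weeks of Screening, and Section 8.2.1.6 has the criteria reviewed again at Visit 2. Criterion 18 does not settle this. Two weeks is shorter than the longest run-in, so antibiotics needed a Baseline rule on any reading. This stands as an ambiguity. It does not close the gap: Section 8.1.5 applies the DH-product window as a look-back at Screening, and nothing tells the site to apply the windows forward.
- **Criterion 4 also covers current use.** Use still going on at Visit 2 is arguably caught. Use that stopped before Visit 2 is not clearly caught.
- **Compliance rules apply.** Section 8.2.1.3 checks adherence at Visit 2. Criterion 9 excludes subjects unwilling or unable to follow Section 5.5, and Section 7.1 requires discontinuation or withdrawal for inability to comply. These bear on product use. However, criterion 9 does not cite Section 6.8, and one past lapse is not plainly unwillingness or inability. Sections 5.5 and 6.7 also spell out milder responses.
- **Baseline qualification filters.** Test teeth must keep the same Schiff score, a tactile threshold of at most 20 g and VAS of at least 40 mm. This removes teeth that improved enough to fail. It keeps those that did not respond.
- **The Section 4.2 rationale is narrower.** It concerns habitual users of anti-sensitivity products. Applying it to a one-off run-in treatment is inference.

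A reader might infer that anyone treated in the run-in is simply free to be randomised. Section 5.5.1, the Visit 2 checks and criteria 9 and 31 do not support that. A reader might also infer that antibiotics alone have a run-in criterion; criteria 6 and 7 show otherwise for rinsing.

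**Conclusion.** The point holds as an inexpensive improvement. For in-office dental and desensitising treatment during the run-in, no clearly worded time-based exclusion applies, and the outcome rests on interpretation and investigator opinion. For DH and bleaching products, the prohibition is clear, but its stated consequences conflict with the 8-week criteria: at most 28 days since use, against at least 70.

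The day counts follow from the documents, taking the look-backs as backward from Screening. The effect on the trial cannot be derived, because the documents do not say how often such exposure occurs or how it alters response. The power figures should therefore not be read as an estimated loss. A reader might also infer a bias favouring one product. Eligibility is settled before allocation, so dilution and noise are expected in the comparison, without a direction toward either arm.

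Criteria 3 and 29a are also timed to Screening but are left out. Criterion 3 also covers current participation in another study, and 29a excludes current or recent caries without a time anchor.

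**What to change.** 1. In Section 5.3, extend criteria 4, 5, 19, 20, 21 and 22 so that, after the Screening window, each adds: *or at any time between Screening and Baseline (Visit 2)*. Criteria 17 and 18 already cover both visits for antibiotics.
2. Reconcile Sections 5.5 and 6.7 and Appendix 15.3 item 1 with the extended criteria. Run-in use of a product with an anti-sensitivity ingredient or DH claim should be an eligibility failure, not a matter for re-instruction or re-appointment.
3. In Section 6.8, refer to the extended criteria so that the consequence of dental treatment before randomisation is stated.

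The change needs no new data or visits. Diaries, videos and changes in treatment are already reviewed at Visit 2 (8.2.1.1, 8.2.1.2). The cost is the rewording and a few more Baseline screen failures. Because exclusion comes before randomisation, the planned 94 completers in each main arm are kept, provided enough subjects are screened.
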